Observational study of the correlation between peripheral Treg cell senescence and serum total cholesterol level

Version: 1.0

Date: December 1st, 2022

Ethics Committee

Tianjin Medical University General hospital

Protocol Abstract

Title	Observational study of the correlation between peripheral Treg cell senescence and serum total cholesterol level
Ethics Committee (Grant Number)	The ethics committee of Tianjin Medical University General Hospital (IRB2022-YX-244-01)
Principal Investigator	[name] (Ph.D.)
Sponsor	Tianjin Medical University General Hospital
Fundings	Natural Science Foundation of China (Grant No. 82071394, 82072166)
Execute Time	12/01/2022-03/31/2023
Recruiting Time	01/01/2023-03/31/2023
Objective	Clarify the correlation between human peripheral Treg cell senescence and serum total cholesterol level
Study Type	Observational
Time Perspective	Cross-Sectional
Enrollment	200 participants
Biospecimen	Description: Whole blood and serum Retention: Samples with DNA
Sampling Method	Probability sample
Condition	Hypercholesterolemia
Inclusion Criteria	1) Age \geq 30 and \leq 60 years old with independent behavior ability. 2) The participants need to fully understand the purpose and content of the study, and voluntarily participate in the study and sign the informed consent.
Exclusion Criteria	1) Pregnant or lactating women. 2) Acute and severe diseases in the last 3 months, including but not limited to, acute myocardial infarction, acute cerebral infarction, cerebral hemorrhage, circulatory failure, respiratory failure (internal diseases), trauma requiring hospitalization, or undergoes surgery under general anesthesia (surgical diseases).

	
3) History of severe diseases, including but not limited to, tumors, serious hematological diseases, serious cardiopulmonary diseases (interventional therapy for coronary artery disease, atrial fibrillation, chronic obstructive pulmonary disease, etc.), renal failure, liver failure, old stroke with serious sequelae.
 
4) Have participated in clinical trials in the past 3 months.
 
5) The investigator considers that not appropriate for inclusion.

Outcome Measures	Treg cell senescence evaluated by the beta-galactosidase (SA-betagal) activity test.
Reference standard	Protocols to detect senescence-associated beta-galactosidase (SA-betagal) activity, a biomarker of senescent cells in culture and in vivo. Nat Protoc 4, 1798-1806, doi:10.1038/nprot.2009.191 (2009)
Statistical Analysis	All statistical analyses were performed using SPSS Statistics Version 27.0 (IBM, Armonk, NY, USA). A two-tailed p value of less than 0.05 was considered to be statistically significant.

1. Research Background and Objectives

Hypercholesterolemia is a risk factor for the occurrence and development of atherosclerosis. Recent animal studies have found that increased serum cholesterol level is associated with peripheral Treg cell senescence, but clinical evidence is still lacking. The purpose of this study is to analyze the correlation between human peripheral Treg cell senescence and serum total cholesterol level using clinical blood samples, thus laying a foundation for the establishment of novel therapeutic strategies for atherosclerosis based on the regulation of Treg cell senescence.

2. Study design

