3.3 Withdrawal criteria

1) The subject decides to withdraw from the study.

2) The doctor or the researcher asks the subject to withdraw from the study (e.g. poor compliance).

4. Study procedure

Researchers initiate the study according to the inclusion/exclusion criteria. After confirming the subject has signed the informed consent, doctors will record the past medical history and medication (especially hypolipidemic drugs) in the past 3 months. Thereafter, an additional 6 ml of venous blood will be drawn during the routine blood tests for examinations of Treg cell senescence.

5. Evaluation Parameters

Treg cell senescence will be evaluated by the beta-galactosidase (SA-betagal) activity test.

6. Withdrawal of the subject

The subject has the right to withdraw from this trial at any time for any reason. The researcher should have a thorough understanding and a record of the reasons for withdrawal. Doctors and researchers also have the right to stop the subject from continuing to participate in the trial at any time during the research. Besides, subjects with early withdrawal should not be replaced by others.

As too many subjects withdrawing from the trial will lead to unreliable results, unnecessary withdrawal should be avoided. The falling rate of the trial should be controlled within 20%.

7. Statistical analysis

1. Pearson correlation coefficient was used to evaluate the correlation between the number of Treg cells in peripheral blood and serum total cholesterol level.

2. Taking the serum total cholesterol level of 5.17 mmol/L as the cut-off value, the subjects were divided into normal cholesterol level group and hypercholesterolemia group. Subsequently, the Propensity Score Matching (PSM) method was used to match the subjects according to gender, age and past medical history, and the Student's t-test was performed to compare the difference of Treg cell senescence between the two groups.

3. The serum total cholesterol level was stratified (e.g., trisection or quartering), and the difference of Treg cell senescence among all groups was compared using one-way ANOVA followed by LSD post-hoc test.

8. Trial Management

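### Section 7 names no primary analysis and leaves the strata open, so the chance of a false-positive result on the study question is about 8% to 11% as written

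*Protocol*

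**What the plan says.** The Protocol Abstract gives a single objective, "Clarify the correlation between human peripheral Treg cell senescence and serum total cholesterol level", and a single outcome measure, "Treg cell senescence evaluated by the beta-galactosidase (SA-betagal) activity test". Its statistical paragraph sets the threshold: "A two-tailed p value of less than 0.05 was considered to be statistically significant".

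Section 7 (Statistical analysis) then lists three analyses:

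- Item 1: "Pearson correlation coefficient was used to evaluate the correlation between the number of Treg cells in peripheral blood and serum total cholesterol level".
- Item 2: "Taking the serum total cholesterol level of 5.17 mmol/L as the cut-off value", subjects are split into two groups and matched by propensity score on gender, age and past medical history. Then a Student's "t-test was performed to compare the difference of Treg cell senescence between the two groups".
- Item 3: "The serum total cholesterol level was stratified (e.g., trisection or quartering"), with one-way ANOVA of senescence across the strata and LSD comparisons afterwards.

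The three items have equal standing. None is called primary, and the protocol does not say which one answers the objective.

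**The concern.** Senescence is tested against cholesterol more than once at 0.05. If any of those tests may support the conclusion, the chance of a spurious finding exceeds the 5% that a reader would attach to one test. The open strata add to this, because tertiles and quartiles of the same data are two different tests.

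No primary analysis can be inferred from the text. Item 1 comes first and matches the objective's word for correlation, but as written it uses a variable that is not the stated outcome. The two items that do use the outcome both cut cholesterol into categories. Followed exactly, Section 7 therefore contains no analysis of the outcome against cholesterol as a continuous variable.

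The analyses can also disagree for ordinary reasons. Item 2 is matched on covariates, while items 1 and 3 are unadjusted. Section 7 does not say what to conclude if they differ.

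**Working it through.** **Inputs from the protocol.** Two-sided 0.05 per test (Abstract); 200 subjects (Abstract and Section 2.2); cut-off 5.17 mmol/L, and three or four strata as examples (Section 7). Section 6 wants losses kept within 20%, so at worst 200 × 0.8 = 160 subjects are analysed.

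**Assumptions not in the protocol.** Cholesterol is normal with mean 4.9 and SD 0.9 or 0.95 mmol/L. Senescence is normal and unrelated to cholesterol. Item 2 is run on unmatched groups, or on groups cut at random to equal size as a stand-in for matching. A false positive means that at least one of the tests in question has p < 0.05. For item 3 that is the overall ANOVA; LSD comparisons are left out.

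**Step 1: the stated level.** In 20,000 null runs, Pearson rejected in 5.2% and the t-test in 5.1%. Across smaller runs each single test rejected in about 4% to 6%. Each test therefore has the level the protocol gives it.

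**Step 2: limits if the tests were independent.**

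- Two tests: 1 − 0.95² = 9.75%.
- Three tests: 1 − 0.95³ = 14.3%.

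Tests of the same outcome on the same subjects are positively correlated, so the real figures should be lower for the same number of tests.

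**Step 3: simulation, n = 200, 20,000 runs.** The ranges cover the unmatched and equal-size versions.

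| Tests that may carry the conclusion | Strata | At least one false positive |
|---|---|---|
| Items 2 and 3 (senescence, as written) | tertiles only | 8.4–8.5% |
| Items 2 and 3 | tertiles and quartiles both tried | 11.1–11.2% |
| Items 1, 2 and 3, item 1 read as senescence | tertiles only | 10.8–10.9% |
| Items 1, 2 and 3, item 1 read as senescence | tertiles and quartiles both tried | 13.1–13.4% |

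Trying both stratifications amounts to a third test in row two and a fourth in row four. The Monte Carlo standard error is about √(0.084 × 0.916 / 20,000) = 0.2 percentage points.

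**Step 4: sensitivity.** Runs of 4,000 replicates varied the cholesterol mean (4.7 or 5.17 mmol/L), the sample size (160 or 200) and the group handling. Rows one and two stayed within about 7% to 10% and 10% to 12%. Rows three and four stayed within about 9% to 11% and 12% to 14%.

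**Step 5: after the fix.** With one pre-named primary test at two-sided 0.05, the error rate for the study question is 5%.

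**The case against.** The strongest reply is that ranking analyses and handling multiplicity are commonly left to a statistical analysis plan, which may exist here but is not shown. That stands as far as a missing multiplicity adjustment goes, and none is requested: this is a cross-sectional observational study. It does not dispose of the point. Section 7 itself fixes the tests, the cut-off, the matching variables and the post-hoc method. In that text it gives three analyses equal standing, leaves the strata to choice, and has no continuous analysis of the stated outcome.

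A second reply is that the protocol never says one significant test is enough, and never claims an overall error of 5%. Both are true. The threshold is per test and each test meets it. The figures above describe what happens if any one test is allowed to carry the conclusion, which the text permits but does not state.

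A reader might go further and say that three tests of the same question give 11% to 15% instead of a promised 5%. The documents do not support that:

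- No overall rate is promised.
- Item 1 as written is not a test of the study question: it is there to "evaluate the correlation between the number of Treg cells in peripheral blood and serum total cholesterol level".
- The 15% end needs both stratifications, which makes four tests, and a Treg count uncorrelated with senescence (15.3% in the simulation).
- The words about all statistical analyses in the Abstract belong to the sentence on software. The threshold sentence is separate, although nothing restricts it.

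Finally, the cholesterol distribution is assumed and real propensity matching was not modelled. This stands as a limit on precision. Changing the mean, the sample size and the group handling moved the results by only a few points.

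**Conclusion.** The point holds as a recommended improvement, not as an error in a stated figure. Under one per-test 0.05 threshold, Section 7 gives no analysis priority for the single objective and leaves the number of strata open.

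Taken as written, two tests address senescence. The chance of at least one false positive is about 8% with fixed tertiles and about 11% if both stratifications can be tried. If Treg number in item 1 is a slip for senescence, it is about 11% for three tests and 13% with both stratifications. A rate more than twice the per-test level is therefore not established for the two tests with fixed tertiles.

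The figures rest on the assumed cholesterol distribution, on 200 subjects, on no real propensity matching, and on any one of the tests being accepted as the answer. They exclude LSD comparisons read without a significant ANOVA, which would raise them.

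**What to change.** In Section 7, and briefly in the Abstract:

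- Name one primary analysis: the association of SA-betagal-measured Treg senescence with serum total cholesterol as a continuous variable, in all evaluable subjects, at two-sided 0.05.
- Fix one number of strata for item 3.
- Label the matched comparison at 5.17 mmol/L and the stratified comparison as supportive, reported with estimates and 95% confidence intervals, and state that neither can carry the conclusion alone.

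This takes a few sentences and uses data already planned, with no added subjects, blood or procedures. The downside is that a significant result in a supportive analysis alone can no longer be claimed as the main finding.

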2.1 Overall design

This research is an observational cross-sectional study.

2.2 Estimated number of subjects

Estimated by statistical analysis, a total of 200 subjects were randomly selected from the population receiving physical examination in the Cadre Physical examination Center of Tianjin Medical University General Hospital from January 2023 to March 2023.

3. Inclusion, Exclusion and Withdrawal Criteria

3.1 Inclusion Criteria

- 1) Age ≥ 30 and ≤ 60 years old with independent behavior ability.
- 2) The participants need to fully understand the purpose and content of the study, and voluntarily participate in the study and sign the informed consent.

3.2 Exclusion Criteria

- 1) Pregnant or lactating women.
- 2) Acute and severe diseases in the last 3 months, including but not limited to, acute myocardial infarction, acute cerebral infarction, cerebral hemorrhage, circulatory failure, respiratory failure (internal diseases), trauma requiring hospitalization, or undergoes surgery under general anesthesia (surgical diseases).
- 3) History of severe diseases, including but not limited to, tumors, serious hematological diseases, serious cardiopulmonary diseases (interventional therapy for coronary artery disease, atrial fibrillation, chronic obstructive pulmonary disease, etc.), renal failure, liver failure, old stroke with serious sequelae.
- 4) Have participated in clinical trials in the past 3 months.

5) The investigator considers that not appropriate for inclusion.

3.3 Withdrawal criteria

1) The subject decides to withdraw from the study.

2) The doctor or the researcher asks the subject to withdraw from the study (e.g. poor compliance).

4. Study procedure

Researchers initiate the study according to the inclusion/exclusion criteria. After confirming the subject has signed the informed consent, doctors will record the past medical history and medication (especially hypolipidemic drugs) in the past 3 months. Thereafter, an additional 6 ml of venous blood will be drawn during the routine blood tests for examinations of Treg cell senescence.

5. Evaluation Parameters

Treg cell senescence will be evaluated by the beta-galactosidase (SA-betagal) activity test.

6. Withdrawal of the subject

The subject has the right to withdraw from this trial at any time for any reason. The researcher should have a thorough understanding and a record of the reasons for withdrawal. Doctors and researchers also have the right to stop the subject from continuing to participate in the trial at any time during the research. Besides, subjects with early withdrawal should not be replaced by others.

As too many subjects withdrawing from the trial will lead to unreliable results, unnecessary withdrawal should be avoided. The falling rate of the trial should be controlled within 20%.

7. Statistical analysis

1. Pearson correlation coefficient was used to evaluate the correlation between the number of Treg cells in peripheral blood and serum total cholesterol level.

2. Taking the serum total cholesterol level of 5.17 mmol/L as the cut-off value, the subjects were divided into normal cholesterol level group and hypercholesterolemia group. Subsequently, the Propensity Score Matching (PSM) method was used to match the subjects according to gender, age and past medical history, and the Student's t-test was performed to compare the difference of Treg cell senescence between the two groups.

3. The serum total cholesterol level was stratified (e.g., trisection or quartering), and the difference of Treg cell senescence among all groups was compared using one-way ANOVA followed by LSD post-hoc test.

8. Trial Management

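### The only correlation analysis uses Treg cell number, while the objective and sole outcome are Treg cell senescence

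*Protocol*

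**What the plan says.** The Objective row of the Protocol Abstract reads "Clarify the correlation between human peripheral Treg cell senescence and serum total cholesterol level". Section 1 repeats the aim: to "analyze the correlation between human peripheral Treg cell senescence and serum total cholesterol level using clinical blood samples". The abstract lists one outcome measure, "Treg cell senescence evaluated by the beta-galactosidase (SA-betagal) activity test", and section 5 lists one evaluation parameter: "Treg cell senescence will be evaluated by the beta-galactosidase (SA-betagal) activity test". Section 4 gives the reason for the study's own blood draw: "an additional 6 ml of venous blood will be drawn during the routine blood tests for examinations of Treg cell senescence".

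Section 7 then sets out three analyses. Item 1 reads: "Pearson correlation coefficient was used to evaluate the correlation between the number of Treg cells in peripheral blood and serum total cholesterol level". Item 2 divides subjects at a total cholesterol of 5.17 mmol/L, matches them by propensity score, and uses a t-test to "compare the difference of Treg cell senescence between the two groups". Item 3 cuts cholesterol into strata, with thirds or quarters as examples, and compares senescence among them by one-way ANOVA with LSD post-hoc tests.

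**The concern.** The number of Treg cells and the senescence of Treg cells are different quantities. A subject can have many Treg cells of which few are senescent, or the reverse. A correlation of cell number with cholesterol therefore does not answer the stated objective, whatever its result.

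Item 1 matters more than its one sentence suggests, because it is the only analysis whose form matches the objective: a correlation coefficient with cholesterol kept continuous. If it is run on another variable, the declared outcome is studied only through cholesterol groups. That yields group differences rather than a coefficient and, for a roughly linear relation, gives up power. It also leaves a published correlation resting on a variable the protocol never declared.

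**Working it through.** **Step 1: the text side by side.**

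| Place in the protocol | Treg variable | Cholesterol |
|---|---|---|
| Title; abstract, Objective; section 1 | senescence | total cholesterol, as a correlation |
| Abstract, Outcome Measures; section 5 | senescence (SA-betagal) | not applicable |
| Section 4, study blood draw | senescence | not applicable |
| Section 7, item 1 | **number of cells** | continuous |
| Section 7, item 2 | senescence | cut at 5.17 mmol/L |
| Section 7, item 3 | senescence | cut into strata |

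No row pairs senescence with continuous cholesterol in an analysis, and no row outside item 1 mentions cell number. The finding rests on this table and on no figure.

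**Step 2: what the missing analysis could detect (illustration).** The plan has no power figure to reproduce. Section 2.2 gives 200 subjects as statistically estimated, without an effect size, SD or power. The inputs from the protocol are n = 200, two-sided 0.05, and section 6: "The falling rate of the trial should be controlled within 20" per cent, without replacement, so n = 200 × 0.8 = 160 at that limit. The correlation r is assumed, as is bivariate normality.

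The Fisher-z power of a Pearson test is Φ(atanh(r)·√(n − 3) − 1.960).

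- n = 200, r = 0.20: 0.2027 × √197 = 0.2027 × 14.036 = 2.845; 2.845 − 1.960 = 0.885; power 0.812.
- n = 160, r = 0.20: 0.2027 × √157 = 0.2027 × 12.530 = 2.540; 2.540 − 1.960 = 0.580; power 0.719.

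The correlation detectable with 80% power is tanh((1.960 + 0.842)/√(n − 3)), which is 0.197 at n = 200 and 0.220 at n = 160.

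**Step 3: the effect of cutting cholesterol.** Splitting a normal variable with a share p above the cut multiplies r by φ(c)/√(p(1 − p)), where c is the normal quantile at 1 − p. The factor is 0.798 for p = 0.5 and 0.759 for p = 0.3. Putting the reduced r into the same power formula, before any loss from matching, gives:

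| n | r | Pearson, uncut | 50/50 split | 30/70 split |
|---|---|---|---|---|
| 200 | 0.15 | 0.56 | 0.39 | 0.36 |
| 200 | 0.20 | 0.81 | 0.62 | 0.57 |
| 200 | 0.25 | 0.95 | 0.81 | 0.77 |
| 160 | 0.15 | 0.47 | 0.33 | 0.30 |
| 160 | 0.20 | 0.72 | 0.52 | 0.48 |
| 160 | 0.25 | 0.89 | 0.72 | 0.67 |

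**Step 4: items 2 and 3 by simulation, at r = 0.20.**

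| Analysis of senescence | n = 200 | n = 160 |
|---|---|---|
| Pearson, cholesterol uncut | 0.81 | 0.72 |
| Item 3, thirds | 0.62 | 0.51 |
| Item 3, quarters | 0.59 | 0.48 |
| Item 2, t-test after 1:1 matching | 0.37 to 0.59 | 0.30 to 0.51 |

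The item 2 range assumes 30% to 50% of subjects above 5.17 mmol/L and 80% to 100% of the smaller group matched. At the lower end with 200 subjects, that is 200 × 0.30 × 0.80 = 48 pairs. Matching is modelled only as loss of subjects.

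**The case against.** The strongest reply is that the question itself is not lost. If correlation in the title is read loosely as association, items 2 and 3 both address it, and item 2 also matches on gender, age and past medical history. No analysis is named as primary, so item 1 does not carry the conclusion alone. This stands, and it limits the seriousness: what is missing is the coefficient and the analysis with uncut cholesterol.

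A second reply is that the wording is a slip for senescent Treg cells, or a deliberate description of cell number before the senescence comparisons. Either is possible and the text settles neither. Items 2 and 3 of the same section write senescence explicitly, so a reader may fairly take item 1 to mean something else. A separate statistical analysis plan could add the missing correlation, but it would not remove the contradiction within the protocol.

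A third reply is that the power figures rest on assumed inputs. That is correct. They move a good deal with r, as the range in the working shows. Item 2 is also an adjusted comparison while the Pearson test is crude, so the figures do not rank those two. The comparison with item 3, which is also crude, is fair under a linear, bivariate normal relation. The finding needs none of these figures.

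**Conclusion.** Item 1 is wrong as written. It applies the plan's only correlation to a variable that is neither the objective nor a declared measurement, and the declared outcome has no correlation analysis. This follows from the text alone and is held with high confidence. Whether it is a drafting slip cannot be told from the protocol.

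It should be fixed, but it does not undermine the study, because senescence is still compared across cholesterol groups. Under the assumed r = 0.20, relying on item 3 in place of an uncut analysis of senescence would lower power by roughly 0.2 (0.81 to 0.62 or 0.59 with 200 subjects; 0.72 to 0.51 or 0.48 with 160). That size depends on the assumed r and on a linear, bivariate normal relation.

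**What to change.** In section 7, item 1, replace the number of Treg cells with Treg cell senescence (SA-betagal activity), so that the correlation is between the declared outcome and total cholesterol. If the intended measure is the count or share of SA-betagal-positive Treg cells, state that in section 5 as the form of the outcome and use the same variable in all three items. If Treg cell number is wanted in its own right, list it as a secondary measure in the abstract and section 5, and keep its correlation as an additional analysis.

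The cost is one sentence of protocol text, plus the submission to the principal investigator and ethics committee that section 8.4 requires for any modification. No new data are needed, since items 2 and 3 already use senescence and total cholesterol.

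### No listed analysis relates Treg senescence to continuous cholesterol: the one correlation uses Treg cell number, and the only adjusted analysis cuts cholesterol at 5.17 mmol/L and matches

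*Protocol*

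**What the plan says.** The Protocol Abstract gives the objective as "Clarify the correlation between human peripheral Treg cell senescence and serum total cholesterol level", and section 1 repeats it: "The purpose of this study is to analyze the correlation between human peripheral Treg cell senescence and serum total cholesterol level". Section 5 names one evaluation parameter: "Treg cell senescence will be evaluated by the beta-galactosidase (SA-betagal) activity test". Treg cell number is not listed as an outcome.

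Section 7 lists three analyses and ranks none of them:

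- **Item 1** is a Pearson coefficient "to evaluate the correlation between the number of Treg cells in peripheral blood and serum total cholesterol level". No adjustment is stated.
- **Item 2** splits the exposure: "Taking the serum total cholesterol level of 5.17 mmol/L as the cut-off value, the subjects were divided into normal cholesterol level group" and a hypercholesterolemia group. Propensity score matching "was used to match the subjects according to gender, age and past medical history", and a Student's t-test then compares senescence. Neither a matching ratio nor a caliper is given.
- **Item 3** cuts cholesterol into strata, with thirds or quarters as examples, and "the difference of Treg cell senescence among all groups was compared using one-way ANOVA followed by LSD post-hoc test". It has no covariates.

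Section 4 adds that "doctors will record the past medical history and medication (especially hypolipidemic drugs) in the past 3 months", so lipid-lowering treatment will be known for each subject, although the matching list does not name it.

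**The concern.** The objective joins two quantities, senescence and total cholesterol level, and calls for their correlation. The only item that computes a correlation, and the only one that leaves cholesterol uncategorised, has a different variable in the place of senescence. An analyst who follows the text would report a coefficient that does not answer the study question.

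Correcting that variable solves half the problem. By matching on gender, age and past medical history in item 2, the protocol itself treats them as confounders. A corrected item 1 would still ignore them, as item 3 does. The adjusted answer would then rest on item 2 alone, which gives up information twice: when cholesterol is reduced to two groups, and again when unmatched subjects are dropped. A modest, roughly linear association would then be more likely to be reported as non-significant than with an adjusted regression on the same subjects.

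**Working it through.** **Text check.** Set against the objective, each item falls short in at least one respect:

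| Section 7 | Outcome | Cholesterol | Confounders controlled |
|---|---|---|---|
| Item 1 | Treg cell number | continuous | no |
| Item 2 | senescence | two groups at 5.17 mmol/L | yes, by matching |
| Item 3 | senescence | strata | no |

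No row combines senescence with continuous cholesterol, with or without adjustment. This step needs no assumption.

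**Inputs for the size of the loss.** From the protocol: N = 200 (section 2.2), two-sided 0.05 (Abstract), and at most 20% loss (section 6), so 200 × 0.8 = 160 evaluable at worst. The protocol states no effect size, SD or power, so its 200 cannot be reproduced. Assumed: normally distributed cholesterol, a linear relation, a slope b in SD of senescence per SD of cholesterol, and a share p above 5.17 mmol/L of 25%, 39% or 50%.

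**Formulas.** Let z be the normal quantile with share p above it and φ(z) the normal density there.

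- Information kept by the cut: k = φ(z)² / [p(1−p)]
- Group difference: d = b·φ(z) / [p(1−p)]
- Within-group SD: s = √(1 − b²k)
- 1:1 matching with everyone above the cut matched: n = min(p, 1−p)·N per group; noncentrality (d/s)·√(n/2), with 2n−2 df
- Continuous cholesterol: noncentrality b·√N / √(1−b²), with N−2 df

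**Numbers at b = 0.20, N = 200.**

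| p | φ(z) | k | d (SD) | n per group | noncentrality | power, 1:1 | power, up to 1:2 | power, all kept |
|---|---|---|---|---|---|---|---|---|
| 25% | 0.318 | 0.539 | 0.339 | 50 | 1.71 | 40% | 50% | 55% |
| 39% | 0.384 | 0.619 | 0.323 | 78 | 2.04 | 53% | 61% | 61% |
| 50% | 0.399 | 0.637 | 0.319 | 100 | 2.29 | 62% | 62% | 62% |

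Continuous cholesterol: 0.20 × √200 / √0.96 = 2.89, power 82%. With three covariates that inflate the slope variance by 5% or 10%, power is 80% or 78%. For comparison, item 3 (noncentral F, equal strata, unadjusted) has 62% with tertiles and 59% with quartiles.

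**Sensitivity, 1:1 matching.**

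| Setting | p = 25% / 39% / 50% | continuous |
|---|---|---|
| b = 0.25, N = 200 | 57% / 72% / 82% | 95% |
| b = 0.30, N = 200 | 73% / 87% / 93% | 99% |
| b = 0.35, N = 200 | 86% / 95% / 98% | about 100% |
| b = 0.20, N = 160 | 33% / 44% / 53% | 73% |
| 0.4 SD step at 5.17, N = 200 | 51% / 70% / 80% | 43% / 57% / 61% |

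In the last row the ranking reverses.

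**Why correcting item 1 is not enough.** A simulation (6000 runs, N = 200) had no true association and one composite covariate that explains 10% of senescence variance and correlates 0.2 or 0.3 with cholesterol. Rejection rates at a nominal 5%:

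- unadjusted Pearson: 14% or 27%
- tertile ANOVA: 10% or 17%
- adjusted regression: 5% or 5%

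**The case against.** The strongest reply is that the contradiction lies only in item 1. Item 2 uses the listed outcome, and the Abstract names hypercholesterolemia as the condition, so comparing subjects above and below a clinical cut is a natural question. Matching and regression are both accepted ways to control confounding, and section 7 never makes item 2 the main analysis. Items 2 and 3 do examine senescence against cholesterol, item 3 over graded levels. Item 1 may be a slip for senescent Treg cells, since section 4 draws the extra blood for senescence testing only. Covariate details and linearity checks often belong in a SAP, which is not shown. Finally, every power figure rests on assumed inputs, and the largest gap (40% against 82%) needs a slope of 0.20, only 25% above the cut and strict 1:1 matching all at once.

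Much of this is fair. The 5.17 mmol/L comparison is legitimate and should stay, and the size of the loss is illustrative. Two things still stand. Slip or not, item 1 names the wrong variable and nothing elsewhere in the protocol corrects it. Nor is this detail left for later: the protocol names its analyses, and none matches its objective. Even with no subject lost to matching, the cut alone costs about 20 points of power or more at a slope of 0.20 (55% / 61% / 62% against 82%).

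**Conclusion.** The concern holds. As written, the correlation in the objective is not estimated, because item 1 uses Treg cell number. That conclusion rests on the text alone. Correcting item 1 would give an unadjusted correlation, and the only adjusted evidence would remain a two-group matched comparison.

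The practical size is conditional. For a weak linear association (0.20 SD per SD, 200 subjects), power is 40–62% with the cut and 1:1 matching, against 78–82% with continuous cholesterol. At 0.35 the gap is small unless few subjects lie above the cut, and under a step at 5.17 mmol/L the matched comparison does better. The slope, the share above the cut, normality and the matching ratio are assumptions, as are the confounder strengths in the simulation. Item 1 is wrong as written; the adjusted regression is a cheap improvement that should be made.

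**What to change.** 1. In section 7, item 1, replace the number of Treg cells with Treg senescence as measured by SA-betagal. If the cell count is also of interest, list it separately as a secondary analysis.
2. Add, as the main adjusted analysis, a linear regression of senescence on continuous total cholesterol in all subjects. Adjust for gender, age and past medical history, with the history conditions named in advance. Use the recorded lipid-lowering medication as a further covariate or in a sensitivity analysis, and check linearity.
3. Keep the matched 5.17 mmol/L comparison and the cholesterol strata as supportive analyses.

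The cost is a wording change through the amendment route in section 8.4, with the same subjects, blood samples, data and software. The one drawback is that a slope assumes approximate linearity and does worse than the group comparison if the true relation is a step at the cut. The linearity check and the retained comparisons cover that case.
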